Sample Size:	
 
• Sleep: change in number of hours and number of restful hours per night over time from month 1 (M1) to M12
 
• Activity level: change in number of steps and minutes of exercise per day over time from M1 to M12
 
• Daily pain scores: change in worst pain of the day (mean value for the month), number of episodes of breakthrough pain (episodes per 7 days), and mean level of breakthrough pain (mean value for month) over time from M1 to M12
 
 
Sample size estimated to be at least 240 WHT patients, 1000 MPM patients, and 150 historic MPP patients. Based on these sample sizes, and assuming a 10% drop-out rate, detectable effect sizes at 80% power for the primary clinical outcomes as analyzed by repeated measures analysis of variance (ANOVA) model and using an omnibus F test (difference in changes between the groups at any time) are:
 
 
• NPS: 0.35 versus MPM; 0.42 versus historic MPP
 
• PHQ-8: 1.40 versus MPM; 1.81 versus historic MPP
 
• MEQs: 11.51 versus MPM; 17.58 versus historic MPP
 

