Statistical Methods:	
For clinical outcomes (primary, secondary, and exploratory), the effects of WHT will be quantified by calculating the change from baseline in clinical outcome variables in the WHT group over 12 months. For primary and secondary outcomes that are measured in the WHT group plus at least 1 control group, generalized linear modeling or nonparametric methods (depending on the score distributions) will be used to compare outcomes across the cohorts. Patient demographic and clinical characteristics that differ between groups at baseline will be included in multivariate adjusted models.
 
Repeated measures models will be used to generate point estimates and 95% confidence intervals (CIs) for least square mean (LSM) differences, odds ratios (ORs), or risk ratios (RRs). Where appropriate an overall F statistic will be generated to compare the change in groups across the study period (interaction of group*time).
 
For the analysis of healthcare utilization, a log-link function with a Poisson or negative binomial distribution will be used. For cost outcomes, a log-link function with a gamma distribution will be used. Otherwise, the same techniques described above (eg, GLM methods to account for matched groups, estimates, and CIs) will be used.
 
For analysis related to clinical outcomes collected only in the WHT group, the effects of WHT will be quantified by calculating the change from baseline over 12 months and using repeated measures ANCOVA models to compare to the null hypothesis (0 change).

-----------------------------	---

**Date of Protocol:** 12 September 2017

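### For the Aim 2 outcomes, change within the WHT group is called the effect of WHT and tested against zero, although every WHT patient is also in the MPP

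*Combined protocol and SAP*

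**What the plan says.** All references are to the Protocol Synopsis of the combined protocol and SAP.

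- **Statistical Methods, last paragraph.** The scope is "For analysis related to clinical outcomes collected only in the WHT group". For these, "the effects of WHT will be quantified by calculating the change from baseline over 12 months", and the test is against zero (the wording is "compare to the null hypothesis (0 change").
- **Outcome Measures, Study Aim 2.** The title presents this aim as comparisons inside the WHT group. It covers sleep, activity and daily pain scores, with change defined "over time from month 1 (M1) to M12".
- **Statistical Methods, opening sentence.** "For clinical outcomes (primary, secondary, and exploratory), the effects of WHT will be quantified by calculating the change from baseline in clinical outcome variables" within the WHT group. The next sentence says that, for primary and secondary outcomes also measured in at least one control group, generalized linear or nonparametric methods "will be used to compare outcomes across the cohorts".
- **Outcome Measures, Study Aim 1.** The primary and secondary clinical endpoints are defined as differences between groups in change from baseline to month 12.
- **Patient Population and Objectives.** WHT patients are those who enter the MPP in a set 12-month window and consent. The objective is whether adding WHT to the MPP improves outcomes.

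**The concern.** The null value of zero is the expected result without WHT only if these patients would not change on the MPP alone. The MPP is itself a treatment programme for chronic pain, so there is no reason to assume that. The test shows whether patients on MPP plus WHT changed. The text calls the answer the effect of WHT, which is a different quantity and the one that the objective asks about.

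Two further wording problems bear on the same point. First, the endpoint definition starts at month 1, when the device is already in use, while the methods refer to baseline. If the endpoint definition governs, the contrast is a trend during use: it misses any change in the first month and can still contain change due to the programme. Second, the opening sentence attaches the within-group label to the primary and secondary outcomes too, which conflicts with their definition under Aim 1.

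At stake is the conclusion drawn from Aim 2. Followed literally, the rule turns any clear change in steps, sleep or daily pain into a stated effect of the device.

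**Working it through.** **1. The plan's own figures.** The Sample Size row gives detectable effects for the between-group comparisons only (for example NPS 0.35 versus MPM and 0.42 versus historic MPP). It gives no power or precision figure for the within-WHT test, so there is nothing to reproduce on this point.

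**2. What the test estimates.** Let B be the change that WHT patients would show on the MPP without WHT (programme effect plus natural course), and W the change that WHT adds.

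- Mean change within the WHT group = B + W.
- The planned null is B + W = 0.
- The objective concerns W, so its null is W = 0.

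The two nulls coincide only if B = 0. A control group with the same B removes it: (B + W) − B = W. No control group has the Aim 2 measurements, so B and W cannot be separated for those outcomes.

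**3. Illustration of size.** Inputs:

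- n = 240 × 0.9 = 216 (Sample Size row: at least 240 WHT patients, 10% drop-out);
- two-sided 5% level (assumed; the documents state 95% CIs but no alpha);
- W = 0;
- d = B divided by the SD of change (assumed, shown as a range);
- a one-sample t test in place of the planned repeated measures model.

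The rejection rate is P(|t| > critical value), where t has n − 1 degrees of freedom and noncentrality d√n, with √216 = 14.70.

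| Background change d (SD) | d√216 | Rejection, n = 216 | Rejection, n = 240 |
|---|---|---|---|
| 0 | 0 | 5% | 5% |
| 0.05 | 0.73 | 11% | 12% |
| 0.10 | 1.47 | 31% | 34% |
| 0.15 | 2.20 | 59% | 64% |
| 0.20 | 2.94 | 83% | 87% |
| 0.30 | 4.41 | 99% | 99.6% |

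Rejection reaches 80% at d = (1.96 + 0.84)/14.70 = 0.19 SD. A comparison with a group that has the same background change would stay at 5% for every d.

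**4. Baseline against month 1.** The methods paragraph refers to change from baseline over 12 months. The Aim 2 endpoint list refers to change from month 1 to month 12, which is 11 months. These are different contrasts. The documents give no value of these measures before WHT use, so the methods paragraph does not say what its baseline would be.

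**5. Opening sentence against Aim 1.** The opening sentence says "the effects of WHT will be quantified by calculating the change from baseline in clinical outcome variables in the WHT group over 12 months". Aim 1 defines the primary and secondary endpoints as differences between groups in that change. In the notation above, the first is B + W. The second is meant to remove B.

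**6. Season.** For an annual cycle of amplitude A, the contrast between months 1 and 12 is at most 2A·sin(π × 11/12) = 0.52A for one patient. It averages to zero if enrolment is even over the 12-month window.

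**The case against.** The strongest reply is that this is a labelling fault in an aim that is openly non-comparative. Aim 2 is titled as a within-group comparison. The primary and secondary endpoints are defined as differences between groups, the primary ones are powered against two controls, and both are analysed across cohorts with a group-by-time test. The historic MPP group is there to address the objective. All of this stands, and it limits the point to Aim 2 and one loose sentence.

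A reader might infer more than the documents support:

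- **That the whole plan measures WHT by within-group change against zero.** It does not. The zero-change test is stated only for outcomes without a control, and no such test is stated for the primary or secondary outcomes.
- **That the planned test has a type I error near 100%.** The test has the right size for its own null. The rates in the working are rejection rates under assumed background changes, and they are modest when those are small.
- **That season drives the result.** Months 1 and 12 fall close together in the calendar and enrolment spans a year, so a cycle largely cancels unless enrolment is uneven. A calendar-month term is not needed on this ground.
- **That regression to the mean is shown to matter.** It is possible, but the documents give no size for it, and starting at month 1 may reduce it.
- **That the device is issued on entry to the MPP.** The documents do not give the timing of one relative to the other.

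It is also fair to say that a 95% CI carries the same information as a two-sided 5% test against zero. Dropping the test therefore matters less than dropping the claim of effect. The replies do not rescue the wording: the methods text calls the within-group result an effect of WHT, and the lack of control data is the reason why it cannot.

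**Conclusion.** The point holds for the Aim 2 outcomes. Change within the WHT group is change on MPP plus WHT. Testing it against zero cannot show an effect of adding WHT. This follows from the design alone and needs no assumption about season, regression to the mean or the timing of device issue.

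The size is illustrative. With no WHT effect, rejection runs from 11% at a background change of 0.05 SD to 99% at 0.30 SD (n = 216). These figures rest on assumed background changes, an assumed 5% level, a simplified test, and a 10% drop-out that the plan states for the primary clinical outcomes and not for device data.

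Two inconsistencies go with it: baseline against month 1 for Aim 2, and the opening sentence of Statistical Methods against the Aim 1 endpoint definitions. No stated figure is shown to be wrong, and the primary and secondary analyses do not change.

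**What to change.** 1. In the opening sentence of Statistical Methods, define the effect of WHT as the WHT-minus-control difference in change, and name the control each time. The historic MPP group is the one that shares the programme; a contrast with MPM also includes the difference between programmes.
2. In the last paragraph, report the Aim 2 outcomes as descriptive change on MPP plus WHT, with an estimate and 95% CI, and make no claim of a WHT effect.
3. Reconcile baseline in that paragraph with month 1 in the Aim 2 endpoint list, and state that no value before WHT is available if that is so.

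The cost is a few sentences, with no new data and no change to the between-group analyses. The sponsor gives up an effect claim for Aim 2 that the design cannot support.
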